7.1 Data Availability Agreement

The Clinical Trail Unit (CTU) of the University Hospital Basel will act as a repository data system. Access to data is granted via formal research enquiry.

8. GCP Statement:

This study has been conducted in compliance with the protocol, the current version of the Declaration of Helsinki, the ICH-GCP or ISO EN 14155 (as far as applicable) as well as all national legal and regulatory requirements.

9. Risks/ Inconveniences, which are study specific:

As Parkinson Patients may suffer from dyskinesia (e.g. rigor, tremor and akinesia), which may affect their movement control and balance, the rhythmic balance-mobility training (rBMT) may potentially put the patients at risk to fall during the intervention. However, there are scaffolds mounted to either side of the rBMT platform, onto which the patient will be holding on to. Furthermore, the research team and therapeutic team will monitor patients during the rBMT as well as the speech-language therapy in order to insure the patients' safety.

10. Benefit for the patient

Through the course of PD patients, both, those who undergo DBS surgery and those who do not, suffer from different degrees of SL performance, which significantly restricts their communication in the society, daily leaving activities and overall quality of life. We anticipate developing and evaluating a possibly preventive or curative therapy considering the patients' SL deficits.

Further, this evaluation will help doctors treating PD patients as well as PD patients to inform (themselves) and choose the therapeutic approach in time regarding the patient's specific needs.

Rationale for the estimated benefit/risk relationship for the patient:

Since the speech-language testing and the interventions per se are non-invasive participating within this study is totally **risk-free** for the patients. Further, there will be no negative consequences whatsoever in case the patient wants to dropout of the study, and dropping-out of the study is possible at any time during the study.

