3. Outcomes	
Primary study outcome: rhythmic abilities in speech and gait (Velocity and Cadence).
 
Secondary study outcome:
 
 • Evaluating the effect of rhythmic interventions on cognition. • Evaluating cortical hemodynamic responses in PD and healthy elderly using functional near-infrared spectroscopy (fNIRS)
4. Study Design:	
Investigator-blinded; Randomized; Controlled; Cross-over.

5. Recruitment

Inclusion Criteria for all groups

- a) The patient is able to cooperate
- b) The patient has the mental competence to provide informed consent to participate in the study
- c) The patient speaks and understands German
- d) The participants are aged between 45-80 yrs. old.

Specific Inclusion Criteria for the DBS Group

- a) Fulfilling the above stated inclusion criteria as stated in a, b, c and d above
- b) The patient is responsive to L-DOPA
- c) Having received or being scheduled for DBS

Exclusion Criteria for all groups

- a) Severe psychiatric disease difficult to treat (compulsive disorder, depression, mania, psychosis, anxiety as outlined in ICD-10 (WHO 2015, current version).
- b) Patient with dementia (DMS-V, MMS<24, MoCa <21)
- c) Secondary Parkinsonism
- d) Age ≤ 18 years
- e) Pregnancy (early onset)
- f) Presence of a known disease other than PD that shortens the life expectancy
- g) Mental incompetence to provide informed consent to participate in the study
- h) Previous intracranial surgery
- i) Epilepsy
- j) Contraindications for DBS seen in MRI-scan (malignant tumors, severe micro vascular disease)
- k) Insufficient skills of German language for participating in neuropsychological evaluations
- l) Sensory problems, severe enough to significantly interfere with neuropsychological assessment
- m) Alcohol and/or drug addiction

5.1 Number of Participants with Power Analysis:	The intended sample size of $N_{\text{total}} = 70$ is based on a small effect size ($\eta^2 = .25$, which is statistically significant increase in the elicitation of words within a certain time) and has been calculated via the statistical programme g*power (power analysis published by the University of Düsseldorf). Further, we expect about 5 drop-outs. Thus, the intended total sample size ($N=70$) may compensate for any possible drop-outs, regardless of group type.
--	---

6. Randomization

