Group 1+2+3 were randomized 1:1:1. As a cross-over designed study, PD patients could swap groups once a therapy- tranche has successfully been completed (i.e. BL, intensive therapy, 4 weeks Follow-up, 6 months Follow-up assessments), see Figure 1.

Group 4 were healthy elderly, who did not receive any therapy and participated once.

- Group 1: rhythmic Speech language Therapy (rSLT)
- Group 2: rhythmic Balance-Mobility Training (rBMT)
- Group 3: 'Waiting List', PD patients receiving no therapy
- Group 4: Healthy Controls (HC)

[figure not shown]

Figure 1. Study Design

7. Testing

Testing took place at baseline (BL), at 4 weeks (T1, directly after the end of intensive treatment) and at 6 months (T2 Follow-up).

a. Medical Examination (only at Baseline)

- i. Medical Examination regarding PD-dementia
- ii. Drug/Alcohol Abuse
- iii. Weight, Height, BMI
- iv. Medications
- v. UPDRS – Unified Parkinson's Disease Rating Scale-I (1/1)
- vi. Modified Neurologic Examination according to Hoehn & Yahr
- vii. Falls Efficiency Scale-1 (FES-1)

i. Speech-Language Tests with simultaneous PRAAT Recording (BL, T1, T2)

- i. Reading 'the northwind and the sun'
- ii. Aachner Aphasia Test (AAT): Spontaneous speech
- iii. AAT: Repeating
- iv. AAT: Naming

- v. Regensburgerwortflüssigkeitstest (RWT) complete
- vi. Comprehension of language-specific cues (Gardenpath Experiment)

b. Motor Tests

- One-leg and Tandem standing test (timed via chronometric stop watch in seconds)
- Parkinson Orientated Mobility Assessment (POMA)
- Walking 6 Meters (timed and counting steps)

c. Near-Infrared Spectroscopy (NIRS) (only at BL)

d. Neuropsychological tests/ psychiatric questionnaires (BL, T1 and T2)

Neuropsychological Tests:

- i. MOCA – Montreal Cognitive Assessment
- ii. Clock Test
- iii. CERAD – Boston Naming Test
- iv. CERAD – Word Retrieval (Animals)
- v. BVL – Basel Verbal Learning Test
- vi. BVL – Basel Verbal Learning Test
- vii. ROCF - Rey-Osterrieth Complex Figure
- viii. BVL - Basel Verbal Learning Test
- ix. BVL - Basel Verbal Learning Test - Recognition
- x. Word retrieval (S-Words)
- xi. TMT - Trail Making Test A
- xii. Trail Making Test B
- xiii. Stroop Test
- xiv. WMS-R - Verbal Digit Span
- xv. WMS-R - Corsi Blocks
- xvi. Mosaik-Test
- xvii. BVMT-R – Brief Visuospatial Memory Test-Revised
- xviii. TAP – Alertness
- xix. TAP - Divided Attention
- xx. Delayed Recall BVMT-R
- xxi. Recognition BVMT-R
- xxii. Tulia

Psychiatric Self-Rating Questionnaires:

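### Section 10 calls participation free of risk while Section 9 names a fall risk in rBMT; separately, the plan specifies no recording of falls or other adverse events

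*Combined protocol and SAP*

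**What the plan says.** **Section 9 (study-specific risks)** says that, because of patients' movement symptoms, rBMT "may potentially put the patients at risk to fall during the intervention". It gives two mitigations: "there are scaffolds mounted to either side of the rBMT platform", and "the research team and therapeutic team will monitor patients during the rBMT as well as the speech-language therapy".

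**Section 10 (benefit for the patient)**, under the rationale for the benefit/risk relationship, argues: "Since the speech-language testing and the interventions per se are non-invasive", "participating within this study is totally risk-free for the patients". No other reason is given. The same section later concedes that benefit from the interventions has not been proven.

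**Section 3 (Outcomes)** names speech and gait rhythm, cognition and fNIRS. It lists no safety outcome.

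**Section 7 (Testing)** places FES-1 in the medical examination block, which is marked as baseline only. It lists no fall count, fall diary or adverse-event form at any visit.

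**The Statistical Analysis section** (also numbered 7) covers ANOVA, correlations and reliable change scores. It contains no analysis of harms.

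**The GCP Statement** (the second section numbered 8) is general and describes no safety reporting procedure.

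**The concern.** There are two separate defects.

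The first is in the text. A benefit/risk rationale that assumes no risk cannot stand beside a section that names one. It is wrong as written for anyone who receives rBMT, whether by first allocation or after a swap of groups. The error matters more because Section 2 presents rBMT as the sham comparator, and the benefit anticipated in Section 10 concerns speech and language. Patients in that arm therefore carry the one named risk, set against a benefit that the document itself calls unproven.

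The second is in the measurement. Followed as written, the plan yields no event data on the one risk it identifies, in the rBMT arm or in the comparison arms. A reader of the results could not tell whether falls happened and went unreported, or did not happen. Section 8 (Interventions) says rBMT was developed with balance and mobility problems in mind, which makes the absence of any fall count more noticeable.

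**Working it through.** The documents give no fall rate, adverse-event count or safety margin, so there is no figure to reproduce. The contradiction is settled by reading; the arithmetic only gives scale.

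**Step 1: the two statements.**
- Section 9: a fall during rBMT is possible, and supports and monitoring are provided.
- Section 10: no risk, because the procedures are non-invasive.
- Non-invasiveness does not bear on falling. Supports and monitoring lower a risk without making it nil. Both statements cannot be true of an rBMT patient.

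**Step 2: search for any specified capture of falls or harms.**
- Outcomes: none.
- Test list: FES-1 only, at baseline. It is a scale, not a count, and it precedes exposure.
- Motor tests (one-leg and tandem standing, POMA, 6 m walk): these measure balance and gait, not falls. The block gives no time points of its own, although the section opening names BL, T1 and T2.
- Questionnaires on mood, fatigue and quality of life: repeated at T1 and T2, but they record states, not events.
- Statistical analysis: no analysis of harms.
- Section 9 monitoring and the GCP Statement: neither describes recording.

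**Step 3: what recorded data could have shown (illustration).**

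Inputs: intended total of 70 (Section 5.1), about 5 expected drop-outs (Section 5.1), and 1:1:1 randomisation of groups 1 to 3 plus a healthy group 4 (Section 6). The document does not say how many of the 70 are healthy controls, so the rBMT arm size is an assumption:
- all 70 in the three randomised arms: 70/3 = 23.3, taken as 23;
- 70 split equally over four groups: 70/4 = 17.5, taken as 17.

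With zero fallers among n patients, the exact one-sided 95% upper limit on the per-patient risk is 1 − 0.05^(1/n); the limit from a two-sided 95% interval is 1 − 0.025^(1/n).

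| n | One-sided upper limit | Two-sided upper limit |
|---|---|---|
| 17 | 16.2% | 19.5% |
| 23 | 12.2% | 14.8% |

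Sensitivity of the one-sided limit:
- with 5 drop-outs, 65/4 ≈ 16 gives 17.1% and 65/3 ≈ 21 gives 13.3%;
- if swaps brought the number exposed to rBMT up to 35, it would be 8.2%;
- even at the extreme of all 70 receiving rBMT, it would be 4.2%.

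Conversely, if the true per-patient fall risk were 5% (an assumed value), the chance of seeing at least one faller would be 1 − 0.95^17 = 58% or 1 − 0.95^23 = 69%.

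**The case against.** The strongest reply is that the document is a synopsis and its silence on event recording is not evidence that nothing was recorded. Staff watched the sessions, and the study is declared GCP-compliant as far as applicable. That stands, and it limits the point. A reader might infer that falls were never recorded; the documents support only that the plan specifies no recording.

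Second, Section 10 is an advance rationale based on non-invasiveness and does not rely on trial data. This also stands. A reader might infer that the missing fall data are what make the risk statement unsupportable. They are not: Section 9 contradicts it whether or not falls were counted.

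Third, the plan does look for deterioration, through repeated questionnaires and negative reliable change scores. True, but worsening on a test score is not a record of events.

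Fourth, falls are not a stated objective, and a fall log in an arm of this size would reveal only a large effect. That is correct. A reader might infer that a log would have shown whether rBMT causes or prevents falls; 17 to 23 patients could not settle that unless the effect were large. The value of a log is descriptive.

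A per-session calculation is also tempting: 3 sessions × 4 weeks × 23 patients = 276 sessions, and 3/276 = 1.1% as the upper limit if no fall occurred. It should not be used. It treats repeated sessions in the same patients as independent, and it fixes the arm at 23.

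**Conclusion.** The point holds in two separate parts. Sections 9 and 10 contradict each other on the risk to rBMT patients; this rests on the text alone and needs no assumption. Independently, the plan specifies no recording or analysis of falls or other adverse events in any arm, and its only fall-related scale precedes exposure.

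The size given, an upper limit of about 16% to 12% per patient after zero fallers, is an illustration. It depends on the assumed 17 to 23 rBMT patients and on treating patients as independent, and swaps would change the number exposed. Its message does not depend on the exact number: no result from a trial of this size could have established the absence of risk.

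Neither part touches the primary comparison of speech and gait. The matter should be corrected, but it does not invalidate the efficacy analysis.

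**What to change.** **For this trial.** The document gives a study end of 22.10.2018 and a last update of 09.10.2019, so nothing can be added to finished visits. The sponsor should:
1. Remove the claim of no risk and make Section 10 agree with Section 9: non-invasive procedures, with a fall risk during rBMT that is reduced by supports and monitoring.
2. State whether and how falls and other adverse events were captured.
3. If they were, report the number of patients with at least one event, by intervention actually received (allowing for swaps), with exact confidence intervals.
4. If they were not, state that no safety conclusion can be drawn.

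**For a future study of this design.** Have the staff who already monitor the sessions record falls and other adverse events. Ask about falls and repeat FES-1 at the existing T1 and T2 visits in all PD arms. Add the per-patient summary in item 3 to the analysis plan.

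**Cost.** For this trial, a text correction and, if records exist, one table; the risk statement becomes less favourable. For a future study, a line on the session sheet and a few minutes per visit. No efficacy analysis changes.
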